5.9.3 Drugs of Abuse Screen

A drugs of abuse screen will be completed according to the laboratory manual provided by the local or central laboratory and according to the Schedule of Events (Table 1).

The drugs of abuse screen will include cotinine, alcohol, amphetamines, barbiturates, cocaine metabolites, opiates, benzodiazepines, and cannabinoids.

5.9.4 C-reactive Protein and other Biomarkers

Separate blood samples (a total of 20 mL) for high sensitivity analysis of CRP will be collected at screening, pre-dose at Day 1, Week 4 and Week 8 (Day -1), and Week 10 (Follow-up).

5.9.5 Sample Collection, Storage, and Shipping

Blood samples for hematology, serum chemistry, coagulation, HIV and hepatitis screens, drugs of abuse screens, and serum hCG will be collected according to the laboratory manual provided by the local or central laboratory and according to the Schedule of Events (Table 1).

5.9.6 Blood Volume

Total blood volume for clinical laboratory tests will be approximately 205 mL.

5.10 Stool Sample

A stool sample will be collected during screening and at Weeks 4 and 8 (Day -1) for the analysis of fecal calprotectin, a biomarker of intestinal inflammatory activity.

5.11 Pharmacokinetic Assessments

Pharmacokinetic samples for the assay of APD371 and metabolites M1 **1** , M2 , and M4 **1** will be collected will be collected at the visit time points indicated in the Schedule of Events (Table 1) and detailed in Pharmacokinetic sampling, Table 3.

Study Day	Blood sampling assessments*
Wk 0 (Day 1)	Prior to and 0.5, 1, 2, 4, 6, 8 (prior to second daily dose), 9
	and 10 hours post first daily dose.
Wk 0 (Day 2)	24 hours post dose first daily dose on Day 1

Wk 2	Prior to first daily dose
Wk 4	Prior to first daily dose
Wk 6	Prior to first daily dose
Wk 8 (Day -1)	Prior to and 0.5, 1, 2, 4, 6, 8 (prior to second daily dose).
Wk 8 (End-of-Treatment)	8 hours post dose first daily dose on Wk 8 (Day-1)

* Allowable windows for sample collection:

- time points up to 4 hours: \pm 5 mins

- time points after 4 hours: ± 15 mins

Total blood volume collected for PK samples will be approximately 100 ml.

A PK sample collection manual will be provided to instruct on the type of anticoagulant to be used, the material supplies, and the sample processing, storage, and shipping procedures.

Plasma samples will be stored at the local laboratory and shipped to the analytical lab for analysis.

At the end of each cohort, biological samples (e.g. plasma) should be packed, labeled, and shipped on dry ice to the designated bioanalytical CRO for analysis. Samples should be shipped in accordance with the hospital SOPs or guidance, and only on a Monday, Tuesday or Wednesday, to minimize the possibility of the samples being in transit over a weekend. If duplicate samples are being shipped, confirmation should be obtained of arrival at the analytical lab of one set of samples before the second set is shipped.

5.12 Adverse Events Assessments

Adverse events will be recorded and reported in accordance with ICH GCP and 22 CFR§312.32. The definitions of AEs and SAEs will be as given in the ICH Topic E2A, ICH Guideline "Note for Guidance on Clinical Safety Data Management: Definitions and Standards for Expedited Reporting."

5.12.1 Adverse Event Reporting

Subjects will be instructed that they may report AEs at any time. Adverse events will be regarded as 'pre-treatment' if they occur between the Screening Visit and the time of administration of the first dose of study medication. All events reported following study medication administration will be recorded as TEAEs.

Monitoring of AEs will be continued up to 30 days after the last study medication administration. In the event that an AE is not resolved or stabilized by this time, the Sponsor in consultation with the Investigator will decide whether to continue to monitor the AE or close-out the event in the database if no further follow-up is necessary.

For this study, an AE is defined as: "Any untoward medical occurrence in a study subject administered any dose of study medication (APD371) and which does not necessarily have to have a causal relationship with this treatment." An AE can therefore be any unfavorable and unintended sign (including an abnormal laboratory finding), symptom, or disease temporally associated with the use of the study medication, whether or not related to the product. AEs can be any of the following:

- Unfavorable changes in general condition;
- Subjective or objective signs/symptoms;
- Concomitant disease or accident;
- Clinically relevant adverse changes in laboratory parameters observed in a subject in the course of a clinical study;
- Pre-existing conditions which worsen in severity or frequency or which have new signs/symptoms associated with them.

Adverse events may be elicited by asking the question: "Since you were last asked, have you felt unwell or different from usual in any way?" Any adverse or unexpected events, signs and symptoms, will be fully recorded on the AE Form including details of severity, onset, duration, outcome and relationship to the drug as determined by the Investigator. Whenever possible, a constellation of signs and symptoms should be recorded as a unifying diagnosis (e.g., self-limited fever, runny nose, cough, and scratchy throat should be captured as an upper respiratory infection rather than by the individual signs and symptoms). Adverse events may also be reported at any time. The type and duration of follow-up of subjects after AEs will be documented.

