3.2 Study Duration and Dates

For each subject, the study duration will last a total of approximately 14 weeks consisting of a screening period of up to 4 weeks, a treatment period of 8 weeks and a follow-up period of two weeks.

[figure not shown]
Subjects will undergo Screening procedures within 29 days prior to dosing. If eligibility is confirmed, subjects will be checked-in at the study site early morning on Day 1, they will overnight at the study site on Day 1 during which they will be randomized, treated with their first dose of APD371 and assessed for safety, tolerability, PK and efficacy. They will then be allowed to return home 6 hours after the first dose of APD371 on Day 2.

The schedule of procedures and visits for the study is provided in Table 1.

[figure not shown]

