5.12.2 Serious Adverse Events and Expedited Reporting of Adverse Events

An SAE is any untoward medical occurrence that at any dose results in the following outcomes:

- Death;
- Is life-threatening;
- Required/prolonged hospitalization;
- Disability/incapacity;
- Congenital anomaly/birth defect;
- Important medical event.

All SAEs will be captured from the time of Screening to 30 days after the dose of study drug, and will be monitored until resolution or stabilization.

An important medical event that may not result in death, be life-threatening, or require hospitalization may be considered an SAE when, based upon appropriate medical judgment, it may jeopardize the subject and may require medical or surgical intervention to prevent one of the outcomes listed in this definition. Examples of such a medical event includes allergic bronchospasm requiring intensive treatment in an emergency room or at home, blood dyscrasias, or convulsions that do not result in in-subject hospitalization, or the development of drug dependency or drug abuse.

Elective hospitalization and/or surgery for clearly pre-existing conditions (for example a surgery that has been scheduled prior to the subject's entry into the study) will not be reported as an SAE. All other hospitalizations, including elective hospitalizations for any condition that was not pre-existing, will be reported as a SAE.

Any AE considered serious by the investigator or which meets SAE criteria must be reported to PPD Pharmacovigilance (PVG) the remote data capture (RDC) system within 24 hours from the time study site personnel first learn about the event. The following contact information is to be used for SAE reporting:

PPD Medical Affairs/Pharmacovigilance PPD PVG Hotline: PPD PVG Fax line:

In the event that the RDC entry is not possible (e.g., system failure or access problems), the study site should complete the paper SAE report form and fax the form to PPD PVG within 24 hours of awareness of the event. The RDC system should be updated as soon as it is available.

A full description of every serious adverse event will need to be provided to PPD PVG (this may be supported by source documentation such as laboratory reports or a discharge summary should the patient be hospitalized).

Other situations as defined in ICH Topic E2A, ICH Guideline, 22 CFR§ 312.32, and EU Volume 10, may also qualify for expedited reporting. In these situations, the process will be as detailed for SAEs above:

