- SAEs which could be associated with the trial procedures;
- SAEs and AEs of special interest including Suspected Unexpected Serious Adverse reactions (SUSARs) that could materially influence the benefit-risk assessment of a medicinal product, such as: a clinically important increase in the rate of a serious suspected adverse reaction over that listed in the Investigator Brochure.

Subjects who become pregnant during the study will be discontinued immediately. Although not considered an SAE or AE, pregnancies occurring during the period of study drug administration (Day 1 to Day 11) until 30 days after the last dose of study drug should be reported to the Sponsor Contact and IRB in the same manner as an SAE.

Pregnancies will be followed every trimester through the first well baby visit. For female partners who become pregnant by male study subjects during the course of the study, reasonable efforts will be made to collect information on the partner's pregnancy through the first well baby visit as provided by the male study subject.

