5.12.9 Follow-up of Adverse Events Present at Last Scheduled Study Visit

Adverse events present at the last study day (Wk8) that require follow-up or a repeat laboratory test will be assessed at the last Follow-up visit (Wk 10) and if still present will

continue to be followed-up for 30 days after the last day of study treatment, according to the CRO's procedures for AE follow-up.

Adverse events that have not resolved or stabilized at 30 days after the last subject's last study dose, will be reviewed with the Sponsor on an individual basis to determine if the database will be locked and subsequently updated once the events of ongoing AEs are resolved or if database lock will be held.

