5.14.1 Handling of Withdrawals

Although a subject is not obliged to give his/her reason for withdrawing prematurely, the Investigator will make a reasonable effort to obtain the reason while fully respecting the subject's rights. If there is a medical reason for withdrawal, the subject will remain under the supervision of the study physician until in satisfactory health. Reasonable efforts will be made to contact a subject who fails to attend any follow-up appointments, in order to ensure that he/she is in satisfactory health.

If a subject is prematurely discontinued from this study, the procedures described in Section 6.4 must be followed.

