6.3 Treatment Period Wk 0 to 8 (Day 1 to Day 56)

Subjects will self-administer APD371 TID for 56 consecutive days according to the randomization schedule. Study procedures will be conducted at the time points indicated in the Schedule of Events (Table 1) and include the following assessments;

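### AEs are to be monitored to 30 days after the last dose, but nothing is scheduled after Week 10, so new events over about 16 of those 30 days rest on spontaneous report

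*Protocol*

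**What the plan says.** Three clauses set a 30-day window after dosing:

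- **AEs** (Protocol 5.12.1): "Monitoring of AEs will be continued up to 30 days after the last study medication administration".
- **SAEs** (Protocol 5.12.2): "All SAEs will be captured from the time of Screening to 30 days after the dose of study drug". This clause does not say that the dose meant is the last one.
- **Pregnancies** (Protocol 5.12.2): the reportable ones are "pregnancies occurring during the period of study drug administration (Day 1 to Day 11) until 30 days after the last dose of study drug".

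The visit schedule is shorter. Section 3.2 plans "a treatment period of 8 weeks and a follow-up period of two weeks". Section 6.3 fixes the dosing period: "Subjects will self-administer APD371 TID for 56 consecutive days according to the randomization schedule". Section 6.5 describes the Week 10 follow-up visit, where AEs are recorded and serum hCG is measured. Section 5.15 allows 2 days either side for the Week 8 and Week 10 visits. No later visit or call appears in the text.

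Section 5.12.9 carries forward events that already exist: "Adverse events present at the last study day (Wk8) that require follow-up or a repeat laboratory test will be assessed at the last Follow-up visit". If they are still present then, they are followed to 30 days after the last treatment day.

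For withdrawals, Section 5.14.1 says: "If a subject is prematurely discontinued from this study, the procedures described in Section 6.4 must be followed". The Section 6.4 list records AEs and serum hCG once and mentions no subsequent contact.

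**The concern.** Tolerability and safety are the primary objective (Protocol 2.1, SAP 2.1). The protocol defines a 30-day collection window but schedules questioning for only about the first half of it. An event that starts after Week 10 is recorded only if the subject takes the inititative, which the 5.12.1 wording permits but does not prompt.

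The consequence carries into the analysis. SAP 9.1 treats every AE after the first dose as a treatment AE and sets no upper time limit, so the less actively questioned period feeds the same TEAE tables as the closely questioned one. With about 8 subjects per cohort, one subject whose only event goes unreported changes a cohort's incidence by 1/8 = 12.5 percentage points.

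Subjects who stop early raise a further question. If their post-dose questioning differs from that of completers, and stopping differs by dose, the two cohorts would be compared on unequal ascertainment.

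**Working it through.** **Inputs**

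- Window: 30 days after the last dose (Protocol 5.12.1).
- Last dosing day: Day 56 (Protocol 4.6 and 6.3).
- Follow-up: two weeks, ending at Week 10, about Day 70 (Protocol 3.2 and 6.5).
- Visit windows: 2 days either side for Week 8 and Week 10 (Protocol 5.15).
- End-of-treatment target: Day 57 (SAP 4.7.2, Table 2).
- Delay from last dose to the early termination visit: not given, so varied below.

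**The plan's own figure.** Screening 4 + treatment 8 + follow-up 2 = 14 weeks, which matches the stated duration. The two-week follow-up therefore leaves no room for a day-30 contact.

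**Formula.** Days without a scheduled question = 30 − (last contact day − last dose day). Share = that number / 30.

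**Completers.** The window closes on Day 56 + 30 = Day 86.

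| Case | Last dose | Last contact | Days without question | Share |
|---|---|---|---|---|
| As planned | 56 | 70 | 30 − 14 = 16 | 53% |
| Follow-up counted from Day 57 | 56 | 71 | 30 − 15 = 15 | 50% |
| Week 10 two days late | 56 | 72 | 30 − 16 = 14 | 47% |
| Week 10 two days early | 56 | 68 | 30 − 12 = 18 | 60% |
| Week 8 early, Week 10 late | 54 | 72 | 30 − 18 = 12 | 40% |
| Week 8 late, Week 10 early | 58 | 68 | 30 − 10 = 20 | 67% |

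The last two rows assume that the last dose moves with the Week 8 visit.

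**Early terminators.** If the Section 6.4 visit is the only contact (an assumption), a visit 0, 3, 7 or 14 days after the last dose leaves 30, 27, 23 or 16 days: 100%, 90%, 77% or 53%. If they also return two weeks after their own last dose, 16 days remain (53%). If instead they attend at calendar Week 10, a subject whose last dose was before Day 40 (70 − 30) would be asked only after the window had closed, by recall.

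These are shares of days, not of events. Turning them into events would need an onset distribution that the documents do not give.

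**The case against.** The other side has several fair points.

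- **Early terminators.** A reader might infer that they have no contact after the termination visit and that their whole window is lost. The documents do not say so. Section 6.5 is not limited to completers. Section 5.14.1 provides for contacting subjects who miss follow-up appointments, and in a section on withdrawals this suggests they may have some. The Schedule of Events (Table 1) is not shown and could settle it. The 100% figure is only an upper bound: it needs a termination visit on the last-dose day and nothing afterwards.
- **Unmonitored time.** A reader might infer that half the window goes unmonitored. That is too broad. Events present at Week 8 and persisting at Week 10 are followed to day 30, SAEs are monitored until they resolve or stabilise, and subjects may report at any time. The gap concerns new-onset events.
- **Bias between doses.** This is possible but not shown. No discontinuation rate is given, and subjects who withdraw for a medical reason stay under physician supervision until well. The study makes no formal hypothesis tests.
- **Pregnancy.** A reader might take the Day 11 in Section 5.12.2 as shortening the reporting window. It does not, because the clause runs on to 30 days after the last dose. Serum hCG is also scheduled at both Week 10 and early termination.

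These points narrow the concern. None supplies a scheduled question for events that begin between Week 10 and day 30 in completers.

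**Conclusion.** The point holds for completers. Following the schedule as written leaves new-onset events over about 16 of 30 days (53%) to spontaneous report. The range is 47% to 60% with the Week 10 window alone, and 40% to 67% if the Week 8 and Week 10 visits shift in opposite directions. This rests on a Day 56 last dose and on the hidden Table 1 adding no later contact.

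For early terminators the finding is one of unclear coverage. The share without a scheduled question could lie anywhere from about 53% to 100%, depending on when the termination visit falls and whether Section 6.5 applies.

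This is a cheap improvement to safety ascertainment worth making, because the stated commitment and the scheduled contacts do not match. It does not show that events were missed or that the dose comparison is biased.

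**What to change.** Add to Protocol Sections 6.4 and 6.5 one structured telephone contact about 30 days after each treated subject's own last dose, whether or not the subject completed treatment. It should use the AE question already in Section 5.12.1 and ask about SAEs and pregnancy. Word Section 3.2 to match. With this call, the share of the window without a scheduled question falls to 0% for both groups. A full extra clinic assessment for early terminators is not needed for this purpose.

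**Cost.** One call for each of at most 20 subjects, and a protocol amendment with IRB approval. The safety cut-off for the last completer moves to about Day 86, 16 days after Week 10. Section 5.12.9 already uses the 30-day point when deciding on database lock, so little added delay is expected.

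Separately, reconcile two passages in Section 5.12.2: the Day 1 to Day 11 administration period against the 56 days of dosing in Sections 4.6 and 6.3, and the SAE window, which omits *last*, against the AE and pregnancy windows, which include it.

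The SAP amendment records that the database has been locked and relocked. For this trial's report, the practical equivalent is to give post-dose follow-up time by cohort and state the limitation.

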5.12.2 Serious Adverse Events and Expedited Reporting of Adverse Events

An SAE is any untoward medical occurrence that at any dose results in the following outcomes:

- Death;
- Is life-threatening;
- Required/prolonged hospitalization;
- Disability/incapacity;
- Congenital anomaly/birth defect;
- Important medical event.

All SAEs will be captured from the time of Screening to 30 days after the dose of study drug, and will be monitored until resolution or stabilization.

An important medical event that may not result in death, be life-threatening, or require hospitalization may be considered an SAE when, based upon appropriate medical judgment, it may jeopardize the subject and may require medical or surgical intervention to prevent one of the outcomes listed in this definition. Examples of such a medical event includes allergic bronchospasm requiring intensive treatment in an emergency room or at home, blood dyscrasias, or convulsions that do not result in in-subject hospitalization, or the development of drug dependency or drug abuse.

Elective hospitalization and/or surgery for clearly pre-existing conditions (for example a surgery that has been scheduled prior to the subject's entry into the study) will not be reported as an SAE. All other hospitalizations, including elective hospitalizations for any condition that was not pre-existing, will be reported as a SAE.

Any AE considered serious by the investigator or which meets SAE criteria must be reported to PPD Pharmacovigilance (PVG) the remote data capture (RDC) system within 24 hours from the time study site personnel first learn about the event. The following contact information is to be used for SAE reporting:

PPD Medical Affairs/Pharmacovigilance PPD PVG Hotline: PPD PVG Fax line:

In the event that the RDC entry is not possible (e.g., system failure or access problems), the study site should complete the paper SAE report form and fax the form to PPD PVG within 24 hours of awareness of the event. The RDC system should be updated as soon as it is available.

A full description of every serious adverse event will need to be provided to PPD PVG (this may be supported by source documentation such as laboratory reports or a discharge summary should the patient be hospitalized).

Other situations as defined in ICH Topic E2A, ICH Guideline, 22 CFR§ 312.32, and EU Volume 10, may also qualify for expedited reporting. In these situations, the process will be as detailed for SAEs above:

- SAEs which could be associated with the trial procedures;
- SAEs and AEs of special interest including Suspected Unexpected Serious Adverse reactions (SUSARs) that could materially influence the benefit-risk assessment of a medicinal product, such as: a clinically important increase in the rate of a serious suspected adverse reaction over that listed in the Investigator Brochure.

Subjects who become pregnant during the study will be discontinued immediately. Although not considered an SAE or AE, pregnancies occurring during the period of study drug administration (Day 1 to Day 11) until 30 days after the last dose of study drug should be reported to the Sponsor Contact and IRB in the same manner as an SAE.

Pregnancies will be followed every trimester through the first well baby visit. For female partners who become pregnant by male study subjects during the course of the study, reasonable efforts will be made to collect information on the partner's pregnancy through the first well baby visit as provided by the male study subject.

5.12.3 Assessment of Adverse Event Severity

The severity of each AE will be assessed at onset by a nurse and/or physician. When recording the outcome of the AE the maximum severity of the AE experienced will also be recorded. The severity of the AE will be graded according to the Common Terminology Criteria for Adverse Events (CTCAE) v4.03¹⁷ definitions, listed below:

Grade 1: Mild; asymptomatic or mild symptoms; clinical or diagnostic observations only; intervention not indicated;

Grade 2: Moderate; minimal, local or noninvasive intervention indicated; limiting age-appropriate instrumental activities of daily living (ADL)*;

Grade 3: Severe or medically significant but not immediately life-threatening; hospitalization or prolongation of hospitalization indicated; disabling; limiting self-care ADL**;

Grade 4: Life-threatening consequences; urgent intervention indicated;

Grade 5: Death related to AE.

*Instrumental ADL refer to preparing meals, shopping for groceries or clothes, using the telephone, managing money, etc.

**Self-care ADL refer to bathing, dressing and undressing, feeding self, using the toilet, taking medications, and not bedridden.

